4.3 Dose Eligibility

4.3.1 CRS-207

Subjects must have adequate organ function as defined by the laboratory values in Table 4 prior to each dosing cycle where CRS-207 is administered. The Study Medical Monitor will be notified of any dose delays due to safety concerns (eg if the subject is recovering from an AE or pembrolizumab infusion reaction) and to discuss a plan to resume treatment. If a dose is delayed beyond 7 days post pembrolizumab, the dose of CRS-207 should be withheld until the next Cycle. If dose is delayed more than 2 weeks, contact the Medical Monitor for further instruction on continued dosing.

Table 4 Dosing Eligibility Requirements for CRS-207

Hematologic	Renal	Hepatic
WBC $\geq 3000/\mu\text{L}$ ANC $\geq 1000/\mu\text{L}$ Platelets $\geq 100,000/\mu\text{L}$ Hemoglobin $\geq 8 \text{ g/dL}$	Creatinine $\leq 1.5 \times \text{ULN}$	AST/ALT $\leq 5 \times \text{ULN}$ Bilirubin $\leq 1.5 \times \text{ULN}$ OR $\leq 3 \times \text{ULN}$ if due to Gilbert's disease
ALT = alanine aminotransferase; ANC = absolute neutrophil count; AST = aspartate aminotransferase; ULN = upper limit of normal; WBC = white blood cell.		

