41. Unwilling or unable to follow the study schedule for any reason

Dose Eligibility

CRS-207

Subjects must have adequate organ function as defined by the laboratory values in the table below prior to each dosing cycle where CRS-207 is administered. The Study Medical Monitor will be notified of any dose delays due to safety concerns (eg if the subject is recovering from an AE or pembrolizumab infusion reaction) and to discuss a plan to resume treatment. If a dose is delayed beyond 7 days post pembrolizumab infusion, the dose of CRS-207 should be withheld until the next Cycle. If a dose is delayed more than 2 weeks, contact the Study Medical Monitor for further instruction on continued dosing.

The dosing eligibility requirements for CRS-207 are as follows:

Hematologic	Renal	Hepatic
WBC ≥3000/μL ANC ≥1000/μL Platelets ≥100,000/μL Hemoglobin ≥8 g/dL	Creatinine ≤1.5 × ULN	AST/ALT ≤5 × ULN Bilirubin ≤ 1.5× ULN OR ≤ 3 × ULN if due to Gilbert's disease
ALT = alanine aminotransferase; ANC = absolute neutrophil count; AST = aspartate aminotransferase; ULN = upper limit of normal; WBC = white blood cell		

Epacadostat & Pembrolizumab

If the subject meets eligibility criteria for the study and is assigned or randomized to receive epacadostat BID and/or pembrolizumab, dosing may initiate and should continue per protocol. The Study Medical Monitor will be notified of any dose interruptions due to safety concerns ([Section 5.4.1](#)).

Pembrolizumab dosing may be delayed up to 2 weeks, after which time it will be considered missed and the subject would continue onto the next scheduled dose. If a dose is delayed more than 2 weeks, contact the Sponsor Medical Monitor for further instruction on continued dosing.

Subject Discontinuation

A subject may be removed from treatment for any of the following reasons:

- Occurrence of an adverse event that presents an unacceptable consequence or risk to the subject
- Subject has received treatment, and there is no longer potential for clinical benefit (treatment should continue beyond initial progression of disease if there is potential for clinical benefit)
- Noncompliance (failure to receive clinical study medication or treatment as mandated by the protocol, or failure to comply with protocol requirements)
- A subject becoming pregnant while on study drug
- Consent is withdrawn by the subject or legal representative
- Study is discontinued by the Sponsor

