9. **Survival Status:** Once a subject has radiographic confirmed PD, discontinues study treatment or starts a new anticancer therapy, the subject moves into the Survival Follow-up phase. Subject will be contacted every 12 weeks (by phone/email is permissible if no recent (with 14 days) medical charting is available) to collect data on survival and any additional cancer-related therapies that may have been administered. Follow-up will continue until death, withdrawal of consent, or the end of the study, whichever occurs first.
10. **Virology** screen will include HIV antibody, hepatitis B (HBsAg), and hepatitis C (HCV-RNA, Qualitative). Virology screen will be performed by the site's local laboratory.
11. **Pregnancy test** is required for women of child bearing potential. Pregnancy testing will be performed by the site's local laboratory.
12. **Safety Labs:** Refer to [Appendix A](#) for complete list of clinical hematology, chemistry analytes. Day 1 blood draws may be taken up to 3 days before dosing with pembrolizumab and then again after the pembrolizumab infusion and before the infusion with CRS-207; additional time points may be obtained if clinically indicated. **To avoid inadvertent contamination of a central line (e.g. infusion ports, PICC lines), blood draws MUST NOT be collected from a central line for at least 4 days after infusion of CRS-207 has started.** If LFTs are found to be abnormal (>Grade 2), frequency of monitoring should be increased to once per week until LFTs have resolved to baseline at which time chemistry test monitoring will be performed according to institutional standards or approximately weekly, whichever is shorter. Liver function does not need to be monitored once per week indefinitely for persistent low-grade abnormalities. Appropriate liver function monitoring intervals should be discussed with the Study Medical Monitor. Hematology, chemistry and liver panel will be performed by the site's local laboratory.
13. **Coagulation panel** will include the following: D-dimer, fibrinogen, INR of PT, and aPTT; and will be collected pre-CRS-207 dose and one day post CRS-207 dose. INR should be monitored weekly for the first 4 weeks after initiation of coumarin-based anticoagulants (see [Section 5.6.2](#) for anticoagulant restrictions) and upon discontinuation of epacadostat. Coagulation testing will be performed by the site's local laboratory. Additional tests should be performed as clinically indicated

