4 SELECTION AND WITHDRAWAL OF SUBJECTS

4.1 Inclusion Criteria

Individuals must meet all of the following requirements to be eligible to enroll in this study:

1. Female, 18 years of age or older
2. Histologically-confirmed disease

For Phase 1: Individuals with epithelial ovarian cancer, fallopian tube carcinoma, or primary peritoneal carcinomas who are considered to have platinum-resistant disease (defined as progression within 6 months from completion of platinum-based chemotherapy). The date should be calculated from the last administered dose of platinum therapy.

For Phase 2: Individuals with epithelial ovarian cancer, fallopian tube carcinoma, or primary peritoneal carcinomas who are considered to have platinum-resistant disease (defined as progression within 6 months from completion of a minimum of 4 platinum therapy cycles). The date should be calculated from the last administered dose of platinum therapy.

3. Measurable disease, as defined by Response Evaluation Criteria in Solid Tumors (RECIST) v1.1

Phase 1 only: Individuals who do not have measurable disease (according to RECIST v1.1) but have assessable disease according to the Gynecologic Cancer Intergroup (GCIg) CA-125 criteria and require treatment, may be included if they meet all other criteria.

4. Agree to provide core tissue biopsies at baseline and at Cycle 2 Day 15
5. Eastern Cooperative Oncology Group (ECOG) performance status of 0 or 1
6. Available archived tumor tissue for central analysis
7. Adequate organ and marrow function, as defined by:
 - White blood cells $\geq 3000/\mu\text{L}$
 - Absolute neutrophil count (ANC) $\geq 1500/\mu\text{L}$
 - Absolute lymphocyte count $\geq 800/\mu\text{L}$
 - Platelet count $\geq 100,000/\mu\text{L}$
 - Serum albumin ≥ 3 g/dL
 - AST and ALT $\leq 2.5 \times$ upper limit of normal (ULN) ($< 5 \times$ ULN for subjects with liver metastases)
 - Total bilirubin \leq the institutional ULN or conjugated bilirubin $\leq 1.2 \times$ ULN (need only be tested if total bilirubin exceeds ULN) or $\leq 3 \times$ institutional ULN if due to Gilbert's disease
 - Serum creatinine $\leq 1.5 \times$ ULN or calculated creatinine clearance (CrCl) (estimated glomerular filtration rate [eGFR] can also be used in place of creatinine or CrCl) > 50 mL/min for serum creatinine $> 1.5 \times$ ULN
 - Hemoglobin ≥ 9 g/dL

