4.3.2 Epacadostat and Pembrolizumab

If the subject meets eligibility criteria for the study and is assigned or randomized to receive epacadostat BID and/or pembrolizumab, dosing may initiate and should continue per protocol. The Study Medical Monitor will be notified of any dose interruptions due to safety concerns ([Section 5.4.1](#)).

Pembrolizumab dosing may be delayed up to 2 weeks, after which time it will be considered missed and the subject would continue onto the next scheduled dose. If a dose is delayed more than 2 weeks, contact the Sponsor Medical Monitor for further instruction on continued dosing.

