6.1 Screening Period

Before screening assessments are conducted, the subject must be given a thorough explanation of the purpose and evaluations of the study. Subsequently, the subject must sign and receive a copy of an ICF that was approved by the Institutional Review Board (IRB) or Ethics Committee and Institutional Biosafety Committee (IBC) and an authorization for use and disclosure of protected health information before any study-specific procedure is performed. The ICF must be obtained before performing any study-specific procedures. However, assessments done as part of standard of care prior to ICF may be used if they are within the required screening period. An original signed consent form will be retained in the subject's source documentation at the site, and a copy will be provided for the subject to take home.

The Screening Period will be up to 28 days. Screening is the interval between the signing of the ICF and the day the subject receives the first dose of treatment in the study (Cycle 1 Day 1). Potential subjects will be evaluated for entry into the study according to the stated inclusion and exclusion criteria. Subjects who are identified during this screening as not eligible for study enrollment do not need to complete all screening procedures. The reason for ineligible status will be documented.

Procedures conducted as part of the subject's routine clinical management (e.g. blood count, imaging study) and obtained before signing of informed consent may be used for screening or baseline purposes provided the procedure meets the protocol-defined criteria and has been performed in the required timeframe of the study (i.e. within 28 days of Cycle 1 Day 1). All information associated with eligibility requirements must be entered into the appropriate eCRF pages.

Tests with results that fail eligibility requirements may be repeated once during the screening period if the Investigator believes the results to be in error. Additionally, a subject who fails screening may repeat the screening process 1 time if the Investigator believes there has been a change in eligibility status (e.g. after recovery from an infection).

The screening biopsy will be obtained once all other eligibility requirements are confirmed. Treatment assignment (Phase 1) or randomization (Phase 2) will be the final step in the screening process, prior to administration of study drug(s).

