10 STATISTICS

10.1 Analysis Populations

The Full Analysis Set (FAS) includes all subjects who received at least 1 dose of study drug. FAS analyses will be conducted on the basis of the randomized treatment. All efficacy analyses will be assessed using the FAS.

A Per-Protocol Set (PPS) will also be used to analyze efficacy endpoints and will be based on study drug exposure (compliance and/or time on study drug) and major protocol deviations. The criteria for inclusion in the PPS will be finalized and documented in the statistical analysis plan (SAP) prior to database lock.

The Safety Set (SAF) includes all randomized subjects who received at least 1 dose of study drug. The SAF will be conducted on the basis of the actual treatment received. All safety analyses will be assessed using the SAF.

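### Two alternative branches of Inclusion Criterion 7 admit subjects whose unchanged creatinine or bilirubin bars them from CRS-207 under Table 4

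*Protocol*

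**What the plan says.** **Entry.** Protocol 4.1, Criterion 7 (repeated in the synopsis) accepts serum creatinine up to 1.5 x ULN. Above that level it accepts a clearance over 50 mL/min instead: "calculated creatinine clearance (CrCl) (estimated glomerular filtration rate [eGFR] can also be used in place of creatinine or CrCl". For bilirubin it accepts total up to ULN, or conjugated up to 1.2 x ULN ("need only be tested if total bilirubin exceeds ULN"), or up to 3 x ULN if due to Gilbert's disease. The conjugated branch puts no ceiling on total bilirubin.

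**Dosing.** Section 4.3.1 states: "Subjects must have adequate organ function as defined by the laboratory values in Table 4 prior to each dosing cycle where CRS-207 is administered". Table 4, like its synopsis copy, requires creatinine at most 1.5 x ULN and bilirubin at most 1.5 x ULN, or 3 x ULN with Gilbert's. It has no clearance alternative and no conjugated alternative.

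**Order of events in Phase 2.** The other drugs are not tied to Table 4. Section 4.3.2 says: "If the subject meets eligibility criteria for the study and is assigned or randomized to receive epacadostat BID and/or pembrolizumab, dosing may initiate". Pembrolizumab is given on Day 1, CRS-207 on Day 2, and epacadostat starts on Day 3. Footnote 12 of Table 1 has Day 1 safety labs drawn "up to 3 days before dosing with pembrolizumab and then again after the pembrolizumab infusion and before the infusion with CRS-207".

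**Biopsy and analysis set.** Section 6.1 says: "The screening biopsy will be obtained once all other eligibility requirements are confirmed". Section 10.1 says: "The Full Analysis Set (FAS) includes all subjects who received at least 1 dose of study drug".

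**The concern.** A dosing gate normally sits at or below the entry standard, so that anyone enrolled can receive the first dose if her labs have not changed. Here two entry branches are looser than the gate, and the gate covers Cycle 1.

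In Phase 2 the gate acts after randomization and after the first pembrolizumab infusion. A subject can therefore enter the Full Analysis Set without ever receiving CRS-207. If she enrols early, she can be one of the first six subjects in a run-in arm whose purpose is to test the combination, and the run-in text neither requires CRS-207 exposure nor provides for replacement. SAP 5.1 and 6.1 would report her safety data under the assigned combination.

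In the Phase 1 CRS-207-alone arm she could undergo a mandatory screening biopsy and then receive no study drug at all.

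**Working it through.** **Step 1: compare every Table 4 analyte with entry.**

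| Analyte | Criterion 7 | Table 4 | Can an eligible subject fail? |
|---|---|---|---|
| WBC (/µL) | ≥3000 | ≥3000 | No |
| ANC (/µL) | ≥1500 | ≥1000 | No |
| Platelets (/µL) | ≥100,000 | ≥100,000 | No |
| Hemoglobin (g/dL) | ≥9 | ≥8 | No |
| AST/ALT | ≤2.5 x ULN (<5 with liver metastases) | ≤5 x ULN | No |
| Creatinine, main limit | ≤1.5 x ULN | ≤1.5 x ULN | No |
| Creatinine, clearance branch | >1.5 x ULN with CrCl/eGFR >50 | ≤1.5 x ULN | **Yes, always** |
| Total bilirubin, main limit | ≤ULN | ≤1.5 x ULN | No |
| Bilirubin, Gilbert's | ≤3 x ULN | ≤3 x ULN | No |
| Bilirubin, conjugated branch | total >ULN, conjugated ≤1.2 x ULN | ≤1.5 x ULN (≤3 with Gilbert's) | **Yes, in part** |

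The renal conflict is complete: the clearance branch is needed only above 1.5 x ULN, so every subject who uses it fails Table 4 on unchanged labs. For example, creatinine 1.51 x ULN with CrCl 51 mL/min passes entry and fails the gate.

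The bilirubin conflict is partial. Total bilirubin above ULN and up to 1.5 x ULN passes both rules. Total of 1.6 x ULN with conjugated 1.2 x ULN and no Gilbert's passes entry and fails the gate. With Gilbert's the conflict starts only above 3 x ULN.

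**Step 2: which bilirubin Table 4 means.** The table says only bilirubin. Appendix A lists total bilirubin, and direct bilirubin only if total is raised at screening. The Gilbert's allowance also fits total. Total is therefore the sensible reading, and the bilirubin half of the finding rests on it; the renal half does not.

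**Step 3: can the renal case occur?** The documents name no clearance formula and no ULN. I assume Cockcroft-Gault for women and a ULN of 0.9 to 1.1 mg/dL:

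CrCl = (140 − age) × kg × 0.85 / (72 × Cr)

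Setting CrCl = 50 and Cr = 1.5 × ULN gives (140 − age) × kg = 50 × 72 × 1.5 × ULN / 0.85, which is 5717.6, 6352.9 and 6988.2 for ULN 0.9, 1.0 and 1.1. Dividing by 90, 80 and 70 gives the weight above which the gap opens:

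| Age | ULN 0.9 | ULN 1.0 | ULN 1.1 |
|---|---|---|---|
| 50 | 63.5 kg | 70.6 kg | 77.6 kg |
| 60 | 71.5 kg | 79.4 kg | 87.4 kg |
| 70 | 81.7 kg | 90.8 kg | 99.8 kg |

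Example: age 50, 90 kg, creatinine 1.6 mg/dL. CrCl = 90 × 90 × 0.85 / (72 × 1.6) = 6885 / 115.2 = 59.8 mL/min, so she is eligible. The Table 4 limit is 1.35 at ULN 0.9 and 1.5 at ULN 1.0, so she fails the gate. At ULN 1.1 the limit is 1.65 and she passes. The same woman with creatinine 1.7 has CrCl = 6885 / 122.4 = 56.25 and fails at that ULN too.

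**Step 4: weight of one subject.** 1/6 = 16.7% of a run-in arm; 1/27 = 3.7% of a full arm.

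**The case against.** The best counter-argument is that sensible conduct would prevent the harm. Screening creatinine and bilirubin are known before randomization, Day 1 labs may be drawn up to three days ahead, and the gate applies before each cycle, so a site could see the problem and hold pembrolizumab. Section 4.3.1 has the Medical Monitor notified of safety-related delays to plan resumption, and contacted after a delay of more than two weeks. The Safety Review Committee, whose members would know she had no CRS-207, may add run-in subjects if at least two subjects in an arm have DLTs. This stands as mitigation but does not remove the conflict. It relies on discretion: 4.3.2 permits pembrolizumab on eligibility alone, and nothing in 4.3.1 waives the Table 4 values.

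Several provisions do reduce the statistical effect:

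- The Per-Protocol Set depends on drug exposure.
- SAP 3.4 counts stage 1 by subjects treated with the CRS-207 dose.
- The Phase 1 DLT window starts at the first CRS-207 dose.
- SAP 9 lists efficacy without summarizing it.
- SAP 3.5 records that development of CRS-207 has ceased.

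It is also fair that the weight table shows possibility, not frequency, and that the bilirubin gap is narrow.

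**Conclusion.** The concern holds, as a minor conflict between two rules. Following the text exactly can give a randomized subject pembrolizumab, with or without epacadostat, while denying her CRS-207 for as long as her labs stay where they were at entry. The renal conflict is certain from the wording. The bilirubin conflict assumes that Table 4 means total bilirubin, which Appendix A supports. The number affected cannot be derived from the documents and is probably small. The weights in the working rest on the assumed formula and ULN range. No stated design figure changes.

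**What to change.** In Criterion 7 (4.1 and the synopsis), require the Table 4 creatinine and bilirubin limits at screening, before the biopsy, assignment or randomization, and Day 1 pembrolizumab. Two edits do this:

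- Delete the CrCl/eGFR alternative for creatinine above 1.5 x ULN.
- Add to the conjugated-bilirubin branch that total bilirubin must be at most 1.5 x ULN, leaving the Gilbert's limit at 3 x ULN.

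The text change is small, but it alters eligibility. It therefore needs a protocol amendment with the usual IRB and IBC approval, and may add a few screen failures among women whose clearance was considered adequate.

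If the sponsor judges these subjects safe to dose, the alternative is to copy both branches into Table 4 and its synopsis copy. That loosens a safety gate for a live bacterial product, so it is a clinical decision rather than an editorial one.

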4.3.2 Epacadostat and Pembrolizumab

If the subject meets eligibility criteria for the study and is assigned or randomized to receive epacadostat BID and/or pembrolizumab, dosing may initiate and should continue per protocol. The Study Medical Monitor will be notified of any dose interruptions due to safety concerns ([Section 5.4.1](#)).

Pembrolizumab dosing may be delayed up to 2 weeks, after which time it will be considered missed and the subject would continue onto the next scheduled dose. If a dose is delayed more than 2 weeks, contact the Sponsor Medical Monitor for further instruction on continued dosing.

4.4 Subject Discontinuation

A subject may be removed from treatment for any of the following reasons:

- Occurrence of an adverse event that presents an unacceptable consequence or risk to the subject
- Subject has received treatment, and there is no longer potential for clinical benefit (treatment should continue beyond initial progression of disease if there is potential for clinical benefit)
- Noncompliance (failure to receive clinical study medication or treatment as mandated by the protocol, or failure to comply with protocol requirements)
- A subject becoming pregnant while on study drug
- Consent is withdrawn by the subject or legal representative
- Study is discontinued by the Sponsor

If a subject provides a baseline biopsy and then subsequently a second biopsy at Cycle 2 Day 15 cannot be obtained due to safety or accessibility issues then the subject may remain on study treatment if they do not otherwise meet the criteria for withdrawal.

Subjects may withdraw consent or discontinue from the study at any time for any reason. Every effort will be made to follow all subjects for PD and survival. If a subject withdraws prematurely from the study due to the above criteria or any other reason, study staff should make every effort to complete the full panel of assessments scheduled for the EOT and Safety Follow-up visits including the post-treatment monitoring for CRS-207. If the EOT Visit occurs >21 days after the last administration of study drug, procedures from the EOT and Safety Follow-up visits may be collected as a single Safety Follow-up Visit. The reason for subject withdrawal must be documented in the electronic Case Report Form (eCRF).

In the case of subjects lost to follow-up, attempts to contact the subject must be made and documented in the subject's study records. Sites will attempt to obtain vital status data (e.g. death or last date known alive) from public records or other external sources where possible if a subject withdraws consent from study (i.e. refuse follow-up for vital status) or is documented as lost to follow up.

5 STUDY TREATMENTS

5.1 Treatment Arms

Subjects will be assigned or randomized to the following treatment arms described in Table 5.

Table 5 ADU-CL-11 Treatment Cycles by Arm

Phase	Arm	Dose ¹ / Route	Treatment Cycle
1	CRS-207	CRS-207: 1×10^9 CFU by IV infusion over ~ 1 hour	CRS-207: Day 1 of each cycle (Cycles 1-6); Q6W thereafter
1	CRS-207/ IDO	CRS-207: 1×10^9 CFU by IV infusion over ~ 1 hour IDO: 100 mg or 300 mg BID Oral	CRS-207: Day 1 of each cycle (Cycles 1-6); Q6W thereafter IDO: BID starting Cycle 1 Day 2
2	CRS-207/ Pembro/ IDO	Pembro: 200 mg by IV infusion over 30 min CRS-207: 1×10^9 CFU by IV infusion over ~ 1 hour IDO: 300 mg Oral BID ¹	Pembro: Day 1 of each cycle CRS-207: Day 2 of each cycle (Cycles 1-6); Q6W thereafter IDO: BID starting Cycle 1 Day 3
2	CRS-207/ Pembro	Pembro: 200 mg by IV infusion over 30 min CRS-207: 1×10^9 CFU by IV infusion over ~ 1 hour	Pembro: Day 1 of each cycle CRS-207: Day 2 of each cycle (Cycles 1-6); Q6W thereafter

BID = twice daily; CFU = colony-forming units; IDO = epacadostat; IV = intravenous; pembro = pembrolizumab; Q6W = once every 6 weeks
¹ RP2D of epacadostat based on Phase 1 dose-evaluation parameters and determined by the SRC; the Phase 2 dose may be further adjusted during Phase 2 Safety Run-in

